2 LIST OF ABBREVIATIONS

AE	Adverse events
ASA	Acetylsalicylic Acid
BI	Boehringer Ingelheim
ATC	Anatomical-Therapeutic-Chemical classification
CHF	Chronic heart failure
DM	Diabetes mellitus
eCRF	Electronic case report form
eGFR	Estimated glomerular filtration rate
Empa	Empagliflozin
EU	European Union
IR	Incidence rate
KM	Kaplan Meier
ITT	Intention to treat
LLA	Lower limb amputation
Max	Maximum
MedDRA	Medical dictionary for regulatory activities
Min	Minimum
PT	Preferred term
SAP	Statistical analysis plan
SAS	Statistical analysis system
SD	Standard deviation
SOC	System organ class
TSAP	Study statistical analysis plan
T1DM	Type 1 diabetes mellitus
T2DM	Type 2 diabetes mellitus
TS	Treated set

3 INTRODUCTION

Following the finalisation of the Art 20 procedure in the EU [EMEA/H/A-20/1442], the potential amputation risk after treatment with empagliflozin should be evaluated as an additional pharmacovigilance activity with a meta-analysis of the two chronic heart failure (CHF) studies 1245.110, 1245.121 together with the EMPA-REG OUTCOME® study 1245.25.

The objective of this SAP is to define the meta-analysis outlined in the PASS protocol 1245.171 and to provide details on individual patient data from studies 1245.25, 1245.110 and 1245.121. All pooled analyses for this meta-analysis will be performed on patient level data. Details on treatment regimens, study intervals, analysis populations and safety analysis on study level are provided in the corresponding TSAPs.

3.1 CLINICAL STUDIES AND STUDY GROUPINGS

3.1.1 Clinical Studies

Individual patient data from the completed EMPA-REG OUTCOME® study 1245.25 and the ongoing/planned studies 1245.110 and 1245.121 see [Table 3.1.1:1](#) below are the basis for the meta-analysis in which the individual patient level data of these three trials are first analysed individually and then pooled together; for study pool definitions see [Table 3.1.2:1](#).

Table 3.1.1:1 Studies included in meta-analysis

No	Study	Title
1	1245.25	A Phase III, multicentre, international, randomized, parallel group, double-blind cardiovascular safety study of BI 10773 (10 mg and 25 mg administered orally once daily) compared to usual care in type 2 diabetes mellitus patients with increased cardiovascular risk
2	1245.110	A phase III randomized, double-blind study to evaluate efficacy and safety of once daily empagliflozin 10 mg compared to placebo, in patients with chronic heart failure with preserved ejection fraction
3	1245.121	A phase III randomized, double-blind study to evaluate efficacy and safety of once daily empagliflozin 10 mg compared to placebo, in patients with chronic heart failure with reduced ejection fraction

3.1.2 Overview of Study Groupings

Since the 3 studies differ concerning their treatment groups and the way amputation risk data were and are captured, two analysis groupings, SAF-M1 and SAF-M2, are arranged to define the most appropriate data sets for the different objectives.

Table 3.1.2: 1

Overview of analysis groupings and individual studies

Grouping	Description	Studies	Purpose
SAF-M1	All studies	1245.25	Frequencies, incidence rates and time to onset of amputation events
		1245.110 1245.121	Frequencies, incidence rates and time to onset for related events based on selected adverse events
SAF-M2	CHF studies	1245.110	Frequencies, incidence rates and time to onset of amputation events
		1245.121	Frequencies, incidence rates and time to onset for related events based on selected adverse events
			Details on lower limb amputations

3.2 STATISTICAL SOFTWARE

SAS® System [REDACTED], version 9.4 (or later) will be used for all statistical analyses.

4 STATISTICAL ANALYSES

The results of the meta-analysis are presented mainly in tabular form. When appropriate, data are presented in graphical form.

Tabulations of frequencies for categorical data will include all different categories and will display the number of observations and the percentage (%) in a category relative to the respective treatment group (Placebo, Empa 10 mg, 25 mg, all Empa). The category "missing" will be displayed if there are actually missing values. Percentages will be based on all patients in the respective patient set whether they have non-missing values or not.

For continuous variables the set of summary statistics in tables is: N (number of patients with non-missing values) / Mean / SD / Min / Q1 (lower quartile) / Median / Q3 (upper quartile) / Max.

4.1 OUTCOMES

In the following sub-sections all endpoints which are relevant for the meta-analysis are described.

AEs will be coded using the most recent version of the MedDRA coding dictionary. The following types of events will be distinguished.

All outcome data is collected over the full trial period even after the first amputation event. We collect all events including recurrent events during the trial period.

4.1.1 Primary Outcomes: Lower Limb Amputation Events

Definition of Lower Limb Amputations Events

In the protocols of the ongoing studies 1245.110 and 1245.121, events leading to LLA are defined as AESIs and include any event leading to a lower-limb procedure of amputation, auto-amputation, or disarticulation. Amputation is defined as a resection of a limb through a bone. Auto-amputation is a spontaneous separation of non-viable portion of the lower limb. Disarticulation is a resection of a limb through a joint. The following procedures are not included in the definition of events leading to LLA: debridement (removal of callus or dead tissue), procedures on a stump (such as stump revision, drainage of an abscess, wound revision, etc.), and other procedures (such as nail resection or removal) without a concomitant resection of a limb (amputation or disarticulation).

For studies 1245.110 and 1245.121 events leading to lower limb amputations (LLA) are considered as AEs of special interest. LLA events are captured on a specific eCRF page.

For study 1245.25 LLA events were not captured systematically. Therefore LLA events were derived based on a medical review of adverse events, concomitant therapy and adverse event narratives. For details see [Appendix 6.2](#).

A major lower limb amputation represents amputation above the ankle (below knee, knee, above knee).

A minor lower limb amputation represents amputation at the ankle and below (ankle, tarsometatarsal, transmetatarsal and toes).

See [Section 4.3.2.2.1](#) for details about the planned analysis.

4.1.2 Secondary Outcomes: Adverse Events Related to Amputation

The term “adverse events related to amputation” is used for events generally known to be related and often preceding amputations. The occurrence of these types of events not necessarily leads to amputation procedures.

[Appendix 6.1](#) contains a list of preferred terms for selecting AEs related to amputation. This list will be reviewed before the conduct of the analysis to ensure that all the PTs are still current in the latest MedDRA version used for the analysis.

This endpoint will be analysed for all patients and for the subset of patients with amputations.

See [Section 4.3.2.2.2](#) for details about the planned analysis.

4.2 ANALYSIS SETS AND HANDLING OF MISSING DATA

All analyses will be based on the treated set (TS).

For study 1245.25 the TS consists of all randomized patients who received at least one dose of study medication. Patients will be assigned to treatment groups according to their randomization.

For studies 1245.110 and 1245.121 the TS will include all patients who were dispensed study medication and were documented to have taken at least one dose of study medication. Patients will be assigned to treatment groups according to their randomization.

Missing amputation dates

In studies 1245.110 and 1245.121, the date and other details on LLA events are to be captured on eCRF pages; therefore no missing dates are expected. However, LLA events were not specifically captured via eCRF in study 1245.25. For any missing date of the LLA event, the date is imputed as the date of admission to the hospital or the date of the diagnosis of the event triggering the amputation, whichever is later.

In case the date information is incomplete (e.g. only year and month are reported), the midpoint of the possible interval is used according to BI standard imputation rules for concomitant therapies.

All missing amputation dates that were imputed will be displayed individually by study, including a narrative justification.

Missing AE onset dates (not applicable for LLA events)

For imputation of missing dates and times BI standards will be used. These are based on a conservative approach. In short, this approach ensures that all AEs with missing dates will be counted as “on-treatment” unless there is well documented data showing otherwise. For the calculation of time to event, the earliest possible date on-treatment (i.e. date of start of treatment) will be used to impute missing onset dates. Partially missing onset dates will also be imputed with the corresponding earliest possible date (e.g. if only the year and month are available, use the first day of the month or the date of start of treatment, whichever is later).

4.3 PLANNED ANALYSES

The following sections describe in detail the statistical analyses planned for disposition, demographic, and baseline characteristics considerations as well as the analyses planned for the safety endpoints described in [Section 4.1](#).

Meta-analysis methods

The meta-analysis will be performed in an exploratory manner. For the main outcomes (time to first LLA and time to first AE related to amputation), a Cox proportional hazards regression model for modelling the time to first event will be used, including the factors study, DM status (T1DM, T2DM, no diabetes) and treatment (all empa vs placebo). Study is assumed as a fixed effect in this meta-analysis.

Frequency analyses

For frequency analyses based on pooled data the estimates for the relative frequency is defined as follows:

$$\hat{p}_j = \frac{\sum_{i=1}^k w_{ji} \cdot \hat{p}_{ji}}{\sum_{i=1}^k w_{ji}}, \text{ where}$$

p_{ji} relative frequency in treatment group j and study (i=1,.., k)

$$w_{ji} = \frac{n_{ji}}{\sum_i n_{ji}}$$

denotes the weight of study i , $i=1, \dots, k$ in treatment group j

n_{ji} number of patients in treatment group j and study i ($i=1, \dots, k$)

Incidence rates

The frequency (%) of AEs does not take into account the duration of treatment. This is particularly important when studies with different treatment durations are pooled for analysis. In this case incidence rates may provide more accurate comparisons among groups.

Incidence rate is the number of new cases of an event occurring in a specified time period divided by the cumulative time at risk. The derivation of time at risk and incidence rates is as follows:

Patients with event:

time at risk in days = date of start of first event – treatment start date + 1

Patients without event:

time at risk in days = last date on treatment + 7 days*(or last date in study for secondary analysis based on ITT approach) – treatment start date + 1

* This is according to the definition of the residual effect period of 7 days as defined in the trial protocols for safety analyses for treatment emergent events.

The incidence rate per 100 patient years can then be calculated as follows:

Incidence rate [1/100 pt-yrs] = 100 * number of patients with event / sum of time at risk over all patients [years].

The estimate for a pooled incidence rate in treatment group j is defined as follows:

$$\widehat{IR}_j = \frac{\sum_{i=1}^k w_{ji} \cdot \widehat{IR}_{ji}}{\sum_{i=1}^k w_{ji}}, \text{ where}$$

\widehat{IR}_{ji} Incidence rate in treatment group j and study ($i=1, \dots, k$)

$$w_{ji} = \frac{t_{ji}}{\sum_i t_{ji}}$$

denotes the weight of study i , $i=1, \dots, k$ in treatment group j

$w_{ji} = \frac{t_{ji}}{\sum_i t_{ji}}$ denotes the weight of study i , $i=1, \dots, k$ in treatment group j

t_{ji} sum of time at risk in treatment group j and study i ($i=1, \dots, k$)

The incidence rates will be calculated with two types of time at risk calculations.

The main analysis is the on-treatment approach where patients are censored at the date of treatment stop + 7 days and the secondary analysis is the ITT analysis where patients are censored at the last day of follow-up if no event occurred.

Time to event analyses

Kaplan Meier (KM) methods of cumulative incidence functions will be performed for time to event data (time to first event).

For pooled data across studies the cumulative incidence functions will be shown overall and stratified by study. The main analysis will be performed with censoring at the date of last study medication intake + 7 days for patients without event. An additional analysis will be performed whereby patients with no events will be censored at the date of last follow-up.

Cox proportional hazards models for modelling time to first event will be applied using factors study, DM status (T1DM, T2DM, no diabetes) and treatment (all empa vs placebo). For treatment comparison, hazard ratios with corresponding 95% confidence intervals as well as corresponding p-values will be presented.

The proportional hazards assumption will be explored by plotting $\log(-\log(\text{survival function}))$ against the log of time by treatment group and checked for parallelism. The interaction of treatment with log of time will be included in the model described above for an exploratory analysis. Further, Schoenfeld residuals for each covariate and treatment will be plotted against time and $\log(\text{time})$.

Competing risk analyses for time to event endpoints

Death is a competing risk for lower limb amputations. A competing risk analysis using a regression model by Fine and Gray (1999) [1] for amputations considering death as a competing event will therefore be performed. The regression model will include the following co-variables: study, diabetes mellitus (T1DM, T2DM, no diabetes), and treatment (empa vs. placebo).

In addition as graphical display a cumulative incidence analysis for amputations and competing event of death will be performed.

The competing risk analysis will be performed according to the standard time to event analysis with censoring at the date of last study medication + 7 days and as additional secondary analysis censored at the date of last follow up.

Trial heterogeneity

In general, some heterogeneity between the studies can be expected due to the different populations involved in the trials to be pooled.

The degree of heterogeneity of the treatment effect between studies will be assessed statistically and clinically/visually.

For time-to-event outcomes, visual inspection of heterogeneity includes a forest plot of the individual study hazard ratios, alongside the corresponding estimate from the individual patient data meta-analysis in SAF-M1 and SAF-M2. For statistical assessment of heterogeneity, a Cox model will be provided including in addition the treatment-by-study interaction term. The p-value of the interaction term from the Cox model in SAF-M1 and SAF-M2 will be used as a statistical measure for heterogeneity.

For binary outcomes (frequencies and incidence rates of LLAs and AEs related to amputation), visual inspection of heterogeneity will be performed using forest plots. These will display the frequencies/incidence rates per treatment arm within each study, alongside the corresponding estimate from the pooled analysis in SAF-M1 and SAF-M2. For statistical assessment of heterogeneity, I^2 will be calculated for the relative risk of an LLA or AEs related to amputation.

If heterogeneity between studies is present, potential sources of variability will be assessed clinically and conclusions outlined in the final report.

Sensitivity analysis for missing dates

For LLA a sensitivity analysis will be conducted for incidence rate calculation in SAF-M1 and SAF-M2 excluding all patients with amputations with missing onset dates. This analysis will only be performed if >10% of onset dates are missing.

Overview of performed analyses

Due to the different study designs not all analyses will be performed for each of the 2 pools. The following table indicates which safety analyses will be performed for which pool and the individually studies.

Table 4.3: 1

Overview of analyses that will be performed for the different study poolings and for the individual study

	Poolings and individual study

Endpoint	SAF-M1	SAF-M2	Study 1245.25	Study 1245.110	Study 1245.121
Disposition, Demographics, Exposure	Yes	Yes	Yes	Yes	Yes
Concomitant diagnoses and therapies	Yes	Yes	Yes	Yes	Yes
Lower limb amputation					
Frequencies	Yes	Yes	Yes	Yes	Yes
Incidence rates	Yes	Yes	Yes	Yes	Yes
Time to onset analyses	Yes	Yes	Yes	Yes	Yes
Time to onset analyses with competing risk	Yes	-	-	-	-
Sensitivity analyses (heterogeneity analyses, forest plot)	Yes	Yes	-	-	-
Adverse events related to amputations (definition based on list of PTs)					
All patients	Yes	Yes	Yes	Yes	Yes
Frequencies	Yes	Yes	Yes	Yes	Yes
Incidence rates	Yes	Yes	Yes	Yes	Yes
Time to onset analyses					
Patients with amputations only, i.e. preceding events					
Frequencies	Yes	Yes	Yes	Yes	Yes
Incidence rates	Yes	Yes	Yes	Yes	Yes
Time to onset analyses (KM only)	Yes	Yes	Yes	Yes	Yes
Lower limb amputation events occurring after the first LLA event					
Descriptive Statistics (Frequency tables with absolute and relative frequencies)	Yes	Yes	Yes	Yes	Yes
Adverse Events related to amputations occurring after the first LLA event					
Descriptive Statistics (Frequency tables with absolute and relative frequencies)	Yes	Yes	Yes	Yes	Yes

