## **6. MILESTONES**

Milestone	Planned Date
IRB/IEC approval	Not applicable for the meta-analysis
Start of data collection	Study 1245.25: 26 August 2010 Study 1245.110: 04 April 2017 Study 1245.121: 21 June 2017
End of data collection	Study 1245.25: 21 April 2015 Study 1245.110: ongoing and event driven, database lock expected in Q3 2021 Study 1245.121: ongoing and event driven, database lock expected in Q3 2020
Final report of study results:	Event driven, final report of the meta-analysis expected in Q3 2022

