### **9.1 STUDY DESIGN**

This is a meta-analysis of 3 studies (1245.25, 1245.110, and 1245.121), which are randomised, placebo-controlled, double-blind, parallel-group, and event-driven studies. A meta-analysis of the 3 studies is considered appropriate to explore the risk for LLA events due to the large study size (approx. 14 000 patients in total in the 3 studies) and long-term exposure (median treatment exposure was 2.6 years in 1245.25; treatment exposure of up to 3 years are expected in ongoing studies 1245.110 and 1245.121). Data from individual patients from the 3 studies, not the result estimates of the 3 studies, will be pooled in the meta-analysis.

[figure not shown]
Study 1245.25 has been completed and the CTR is available [[c02695839](#)]. The study title is “A Phase III, multicentre, international, randomised, parallel group, double blind cardiovascular safety study of BI 10773 (10 mg and 25 mg administered orally once daily) compared to usual care in type 2 diabetes mellitus patients with increased cardiovascular risk”.

Study 1245.110 and 1245.121 are ongoing and the CTPs are available [[c03946327](#), [c09098452](#)]. The study title of 1245.110 is “A phase III randomised, double-blind trial to evaluate efficacy and safety of once daily empagliflozin 10 mg compared to placebo, in patients with chronic heart failure with preserved ejection fraction”. The study title of 1245.121 is “A phase III randomised, double-blind trial to evaluate efficacy and safety of once daily empagliflozin 10 mg compared to placebo, in patients with chronic heart failure with reduced ejection fraction”.

The overall designs of the studies are shown in [Figure 9.1: 1](#).

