### **9.7.1 Main analysis**

LLA events (primary outcome) and AEs related to amputation (secondary outcome) will be analysed using frequency analyses, incidence rates, Kaplan-Meier estimates, and Cox proportional hazards models to compare empagliflozin with placebo in the pooled populations of SAF-M1, SAF-M2, and for each of the 3 studies (1245.25, 1245.110, and 1245.121) separately. Kaplan-Meier analyses (cumulative incidence functions) for time to first event will be provided by treatment and stratified by study.

Cox proportional hazards models will include the factors study, diabetes mellitus status (T1DM, T2DM, no diabetes), and treatment (all empa vs placebo).

As the primary analysis, the “on-treatment” approach will include events with an onset date within the treatment period (from first to last dose of study medication plus 7 days to account for the residual drug effect).

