Considering the potential differences in patient populations, subgroup analyses by demographic and baseline conditions will be carried out to assess any potential impact of these differences on the results (see [Section 9.3.3](#)).

For study 1245.25, LLA-related events were not pre-specified in the protocol or specifically captured on eCRF pages (see [Section 9.3.2.1](#)). Therefore, the extent of reporting may be different from studies 1245.110 and 1245.121. As details on LLA events collected in studies 1245.110 and 1245.121 (the reasons leading to LLA, the number of LLA episodes, level of LLA, etc.) are not available in 1245.25, SAF-M2 is created for the purpose of analysing these specific details.

Although approx. 14 000 patients are expected to be included in this meta-analysis (see [Section 9.5](#)), the number of studies involved is low ( $N=3$ ). The 3 studies were designed to investigate empagliflozin's effect on cardiovascular events, and not specifically designed or powered to investigate LLA events. As all 3 studies are event-driven, duration of treatment and observation will be different for each patient, which will be taken into account using "time at risk" to adjust the incidence of outcomes (see [Section 9.3.1](#)). As all 3 studies investigate patients who meet the specific study entry criteria, the patients in this meta-analysis may not exactly reflect the circumstances in which empagliflozin is used in the routine clinical practice, thereby limiting the generalisability of the results.

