4.3.2.2.1 Lower limb amputation

Frequency tables of patients with LLA (see [Section 4.1.1.1](#)) by treatment, SOC and PT will be provided. In addition incidence rates will be displayed.

Kaplan Meier analyses (cumulative incidence functions) for time to first LLA will be provided by treatment and stratified by study if feasible. Cumulative proportion of patients and the number of patients "at risk" will be provided.

The number of LLA episodes per patients will be summarized in a frequency table. Additionally a listing of patients with recurrent events will be provided.

For SAF-M2 the following analyses will be performed additionally:

- Frequencies of reasons leading to the LLA
- Number of LLA episodes per patient
- Number of LLA episodes per patient excluding those due to trauma and tumor
- Level of amputation for the first LLA, excluding amputation due to trauma and tumor (highest)
- Number of patients having a major LLA as first LLA
- Number of patients with any major LLA
- Number of patients having a knee or above knee LLA as first LLA
- Number of patients with any knee or above knee LLA

Descriptive statistics will be provided to summarize all amputation events occurring after the first LLA event.

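### The pooled SAF-M1 Kaplan-Meier and competing-risk curves have no cut-off or standardisation, so a changing trial mix can bend them if rates differ between trials

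*SAP*

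**What the plan says.** SAP 4.3 (time to event analyses) plans, for time to first event: "For pooled data across studies the cumulative incidence functions will be shown overall and stratified by study". It gives no end time for the overall curve and no weighting or standardisation by trial.

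Three places differ on the by-study display. SAP 4.3 promises it alongside the overall curve. Protocol 9.7.1 names only the by-study form: "Kaplan-Meier analyses (cumulative incidence functions) for time to first event will be provided by treatment and stratified by study". SAP 4.3.2.2.1 makes it conditional for the primary outcome: "Kaplan Meier analyses (cumulative incidence functions) for time to first LLA will be provided by treatment and stratified by study if feasible".

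For competing risks, SAP 4.3 adds: "In addition as graphical display a cumulative incidence analysis for amputations and competing event of death will be performed". Protocol Table 9.7: 2 and SAP Table 4.3: 1 plan this analysis for SAF-M1 only, with a dash for SAF-M2 and for each single study. No by-study display is stated.

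On follow-up, Protocol 9.1 says: "median treatment exposure was 2.6 years in 1245.25; treatment exposure of up to 3 years are expected in ongoing studies 1245.110 and 1245.121". On capture, LLA in 1245.25 was found by retrospective search and medical review (SAP 4.1.1 and Appendix 6.2), whereas the heart-failure trials use a dedicated eCRF page. Protocol 9.9 accepts the consequence: "Therefore, the extent of reporting may be different from studies 1245.110 and 1245.121".

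**The concern.** A Kaplan-Meier or cumulative incidence curve drawn from pooled patients needs censoring to be unrelated to risk. Here the trial determines how long a patient can be followed, and it may also determine the observed rate, through the population (type 2 diabetes with cardiovascular risk, or heart failure with or without diabetes) and through the capture method. If so, the patients still at risk late in the curve come increasingly from 1245.25, and the slope drifts towards that trial's rate. The late part of the curve then describes neither the pooled population nor, read from time zero, any one trial.

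The question is about long-term exposure, so a late bend is what a reader would interpret. The competing-risk plot is the more exposed of the two, because the same mechanism acts on the death curve and no by-study version is planned beside it. The log(-log) check of proportional hazards is also to be drawn by treatment group with no mention of study. If it uses the same pooled curves, it could depart from parallel with no drug effect.

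**Working it through.** **Plan's own figure.** Trial sizes from Protocol 9.5: 2345 + 2342 + 2333 = 7020, and 7020 + 4126 + 2850 = 13,996. This reproduces the stated total of approximately 14 000.

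**Starting mix.** Share of 1245.25 at day 0: empagliflozin 4687/8175 = 57.3%; placebo 2333/5821 = 40.1%; both arms together 7020/13,996 = 50.2%.

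**Possible follow-up, from Protocol section 6.** 1245.25 runs from 26 August 2010 to an end of data collection given as "Study 1245.25: 21 April 2015", a span of 4.65 years. 1245.110 runs from 4 April 2017 to a lock in Q3 2021, 4.24 to 4.49 years. 1245.121 runs from 21 June 2017 to a lock in Q3 2020, 3.03 to 3.28 years. These are upper limits on follow-up. The 1245.110 span does not agree with the 3-year text in Protocol 9.1, so both readings are carried below.

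**Assumptions (not in the documents).**
- Constant LLA hazard in each trial and no drug effect.
- 1 per 100 patient-years in 1245.25; heart-failure rate half or double that.
- Uniform follow-up: 1245.25 over 0.9-4.3 years (median 2.6), 1245.110 over 1-3 years, 1245.121 over 0.5-3 years.
- Second reading: 1245.110 over 1-4.1 years.

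**Formulas.** With n_i patients in the arm, G_i(t) the share not yet censored, and S_i(t) = exp(-h_i t):
- pooled hazard h(t) = sum(n_i G_i S_i h_i) / sum(n_i G_i S_i)
- pooled curve = 1 - exp(-integral of h)
- reference curve = sum of w_i (1 - exp(-h_i t)), with w_i a fixed trial mix

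**Mix over time (3-year reading, half rate).** Share of risk time under eCRF capture in years 1 to 4: placebo 60%, 56%, 40%, 0%; empagliflozin 42%, 39%, 25%, 0%. The apparent placebo rate rises from 0.70 to 1.00 per 100 patient-years and the empagliflozin rate from 0.79 to 1.00, although no hazard changes. With the double rate, placebo falls from 1.59 to 1.00 and empagliflozin from 1.42 to 1.00.

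**Reference at 4 years, half rate.** 1 - exp(-0.04) = 3.921% and 1 - exp(-0.02) = 1.980%.
- Placebo, own mix: 0.401 × 3.921 + 0.599 × 1.980 = 2.76%.
- Empagliflozin, own mix: 0.573 × 3.921 + 0.427 × 1.980 = 3.09%.
- Common mix for both arms: 0.502 × 3.921 + 0.498 × 1.980 = 2.95%.

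For the double rate, 1 - exp(-0.08) = 7.688% replaces 1.980%, giving 6.18%, 5.53% and 5.80%.

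**Pooled curve at 4 years against each arm's own day-0 mix.**

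| Reading | Heart-failure rate | Placebo | Empagliflozin |
|---|---|---|---|
| Both stop at 3 years | half | 3.20% vs 2.76% (+16%) | 3.43% vs 3.09% (+11%) |
| Both stop at 3 years | double | 5.34% vs 6.18% (-13%) | 4.89% vs 5.53% (-11%) |
| 1245.110 to 4.1 years | half | 2.91% vs 2.76% (about +5%) | 3.23% vs 3.09% (about +5%) |
| 1245.110 to 4.1 years | double | 5.89% vs 6.18% (about -5%) | 5.26% vs 5.53% (about -5%) |

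For the first row the absolute error is 3.20 - 2.76 = 0.44 points (placebo) and 3.43 - 3.09 = 0.34 points (empagliflozin). At 3 years the placebo error on that row is about 0.15 points (2.223% against 2.077%).

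**Against the common mix (3-year reading, half rate).** Placebo 3.20/2.95 is about +8%; empagliflozin 3.43/2.95 is about +16%. Part of this comes from the arms' different starting mixes (57% against 40%), not from the change over time.

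**Equal rates.** h(t) is constant and every error is zero.

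**The case against.** The case against has several parts, and much of it stands.

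- A reader might infer that the late curve is bent by design. The documents do not support that. They give no LLA rates, and Protocol 9.9 says only that reporting may differ. Without a rate difference there is no bend, so size and direction are unknown.
- A reader might infer that the late curve is 1245.25 alone. That follows from the 3-year text but not from the milestones, under which 1245.110 could contribute past year 4 and the change in mix would be gradual.
- A reader might infer that the treatment comparison is biased. It is not affected by this mechanism: the Cox and Fine-Gray models both include study, and the whole exercise is exploratory.
- The absolute errors are small. On the half-rate, 3-year reading, only about 198 of 5821 placebo patients remain at risk at year 4, and the standard error there is roughly 0.5 points, larger than the 0.44-point bias.
- Much is already planned: by-study Kaplan-Meier curves, single-trial and SAF-M2 time-to-onset analyses, numbers at risk, and an open statement of the differences between trials.

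Three gaps remain. The competing-risk plot has no by-study counterpart, the LLA section makes by-study curves conditional, and no pooled curve has a stopping rule or a fixed trial mix.

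**Conclusion.** The point holds in a conditional form. The overall SAF-M1 Kaplan-Meier curve and the competing-risk plot mix trials whose shares change with time on drug, and they will bend if observed LLA or death rates differ between trials. With a heart-failure rate half or double an assumed 1 per 100 patient-years, the 4-year error against each arm's own starting mix is about 11-16% on the 3-year reading and about 5% if 1245.110 runs to about 4 years. On the half-rate, 3-year reading that is about 0.3-0.4 percentage points. Against one common mix it is about 8% for placebo and 16% for empagliflozin. All of this rests on assumed rates and assumed follow-up shapes. It concerns descriptive plots only and is minor to moderate. The competing-risk plot deserves most attention, because as planned nothing by study stands beside it.

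**What to change.** In SAP 4.3 and 4.3.2.2.1, and in Protocol 9.7.1 and 9.7.2.1:

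1. Show the competing-risk cumulative incidence of LLA and of death by study as well as pooled, and amend the two overview tables to match.
2. Delete the words *if feasible* in SAP 4.3.2.2.1, so that by-study Kaplan-Meier curves are always shown.
3. Standardise the pooled SAF-M1 curves: estimate Kaplan-Meier or Aalen-Johansen curves by study and arm, then average them with one fixed set of study weights (for example each trial's share of all treated patients) used for both arms. End the pooled curve when any trial's number at risk falls below a pre-set level, for example 10% of its treated patients, and show later time for the remaining trial or trials only. This rule works whichever follow-up figure proves right.
4. Print numbers at risk by trial, draw the log(-log) plot by study, and reconcile the 3-year text in Protocol 9.1 with the 1245.110 milestones in section 6.

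The cost is SAP and protocol wording and a little programming, with no new data. The downside is that the pooled curve ends earlier, and later follow-up appears only in the panels of the trials still contributing.
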